6.3.1. Solicited Local and Systemic Adverse Events

Solicited AEs will be captured at study visits and by a diary distributed to participants. Thermometers and rulers will be provided to participants for evaluating AEs. Text and/or phone reminders to complete the solicited AE diary may be provided to participants.

Solicited local AEs to be assessed include redness, firmness, swelling, pain or itching at the injection site, medication taken for pain after IM administration, tingling/numbness, and bleeding or bruising at the injection site after IM administration. Solicited systemic AEs to be assessed include chills, nausea, vomiting, diarrhea, headache, fatigue, myalgia, abdominal discomfort/pain, joint pain, and fever. The solicited AE diary may be either electronic diary (eDiary) or a paper diary, as available. A sample diary for collecting solicited AEs is provided in [Appendix 1](#).

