7.4.1. Severity/Intensity

The severity/intensity of AEs and SAEs will be graded based upon the participant's symptoms in accordance with the Guidance for Industry: Toxicity Grading Scale for Healthy Adult and Adolescent Volunteers Enrolled in Preventive Vaccine Clinical Trials (2007).

AEs that are not defined in the Guidance for Industry: Toxicity Grading Scale for Healthy Adult and Adolescent Volunteers Enrolled in Preventive Vaccine Clinical Trials (2007) should be evaluated for severity/intensity according to the following scale:

- Grade 1 = Mild: transient or mild discomfort, no limitation in activity; no medical intervention/therapy required.
- Grade 2 = Moderate: mild to moderate limitation in activity, some assistance may be needed; no or minimal medical intervention/therapy required.
- Grade 3 = Severe: marked limitation in activity, some assistance usually required; medical intervention/therapy required, hospitalization possible.
- Grade 4 = Life threatening: extreme limitation in activity, significant assistance required; significant medical intervention/therapy required, hospitalization or hospice care probable.
- Grade 5 = Death: the event results in death.

It is important to distinguish between serious and severe AEs. Severity is a measure of intensity, whereas seriousness is defined by the criteria under [Section 7.3](#). An AE of severe intensity may not be considered serious. Seriousness, not severity, serves as a guide for defining regulatory obligations.

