7.8.2. Phase 1 Study Toxicity Study Stopping Rules

Safety will be monitored throughout the study.

In the phase 1 study, the first 7 days after vaccine administration are defined as the toxicity assessment period. The SRC will also review each treatment-related SAE and toxicity, during the toxicity assessment period and each treatment-related SAE and grade ≥ 3 AE after the toxicity assessment period, to determine if the event warrants stopping the trial, modifying the trial, or continuing without modification. In the event of a death that is suspected to be related to the treatment regimen, further enrollment will be delayed until the SRC approves continuation of enrollment in order to allow for proper review and notification to the IRB and the SAHPRA. In the event of a pause in clinical trial enrollment due to toxicity, both the SRC and the SAHPRA will be notified.

Stopping/pausing guidelines are predefined criteria that halt the conduct of a study. Toxicities that may warrant stopping of the trial, based on SAHPRA guidance and with grading scales from the Guidance for Industry: Toxicity Grading Scale for Healthy Adult and Adolescent Volunteers Enrolled in Preventive Vaccine Clinical Trials (2007) (see [Section 7.1](#)), include the following:

1. If 1 or more participants experience a Grade 4 AE ([Section 7.1](#)), vital sign or laboratory abnormality that is judged related to study vaccine, all vaccinations will be suspended until a full safety review is performed.
2. If 3 or more participants report the same or similar Grade 3 solicited AE, unsolicited AE, or clinically relevant laboratory abnormality judged related to the study vaccine, all vaccinations will be suspended until a full safety review is performed.
3. The study will be halted (no new enrollments and no further investigational product administered until a full safety review and consultation with the health authorities completed) if one of the following occurs:
 - a. One participant experiences an SAE judged related to the study vaccine, or
 - b. There is a participant death judged related to the study vaccine.

If any of the halting rules are met, vaccination of participants will be suspended until after full review of safety data by the SRC. The Investigator must inform the Sponsor and IRB if any of the halting rules are met. The Sponsor then must inform the SRC and SAHPRA.

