4. Have you experienced any pain or itching at the injection site?	Check:  Pain  Itch or  No Pain/Itch Circle mild, moderate or severe	 Pain  Itch Mild Mild Mod Mod Severe Severe  No Pain/Itch	 Pain  Itch Mild Mild Mod Mod Severe Severe  No Pain/Itch	 Pain  Itch Mild Mild Mod Mod Severe Severe  No Pain/Itch	 Pain  Itch Mild Mild Mod Mod Severe Severe  No Pain/Itch	 Pain  Itch Mild Mild Mod Mod Severe Severe  No Pain/Itch	 Pain  Itch Mild Mild Mod Mod Severe Severe  No Pain/Itch	 Pain  Itch Mild Mild Mod Mod Severe Severe  No Pain/Itch
5. Have you taken or applied any medication for injection site pain or itching?	Check:  Yes or  No Provide name of medication(s)	 Yes or  No Name(s):						
6. Is there tingling or numbness at the injection site?	Check:  Yes or  No	 Yes or  No	 Yes or  No	 Yes or  No	 Yes or  No	 Yes or  No	 Yes or  No	 Yes or  No
7. Is there bleeding at the injection site?	Check:  Yes or  No	 Yes or  No	 Yes or  No	 Yes or  No	 Yes or  No	 Yes or  No	 Yes or  No	 Yes or  No

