| 6. Have you experienced any fatigue? | Check:
 Yes or  No
If yes, tell us if the fatigue is mild, moderate or severe |  Yes or  No
Mild
Moderate
Severe |
| 7. Have you experienced any muscle pain? | Check:
 Yes or  No
If yes, tell us if the muscle pain is mild, moderate or severe |  Yes or  No
Mild
Moderate
Severe |
| 8. Have you experienced any abdominal discomfort/pain? | Check:
 Yes or  No
If yes, tell us if the abdominal discomfort/pain is mild, moderate or severe |  Yes or  No
Mild
Moderate
Severe |
| 9. Have you experienced any joint pain? | Check:
 Yes or  No
If yes, tell us if the joint pain is mild, moderate or severe |  Yes or  No
Mild
Moderate
Severe |

STUDY NUMBER*:

| Solicited systemic AEs | Instructions | Date / / |
|---|---|---------------------------------------|---------------------------------------|---------------------------------------|---------------------------------------|---------------------------------------|---------------------------------------|---------------------------------------|
| 10. Record your daily temperature upon waking (do not drink anything 5 minutes before taking your temperature) | Fill in the temperature and time:
If your temperature is 38°C for more than 24 hours, call your doctor | ____ °C
Time:
____ :
AM / PM |

Grading Chills:

Mild: Mild sensation of cold, shivering, chattering of teeth
 Moderate: Moderate tremor of entire body, medication taken
 Severe: Prolonged or severe, does not respond to medication

Grading Nausea and Vomiting:

Mild: No interference with activity or 1 – 2 episodes/24 hours
 Moderate: Some interference with activity or > 2 episodes/24 hours
 Severe: Prevents daily activity, requires outpatient IV hydration

Grading Diarrhea:

Mild: 2 – 3 loose stools or < 400 gms/24 hours
 Moderate: 4 – 5 stools or 400 – 800 gms/24 hours
 Severe: 6 or more watery stools or > 800 gms/24 hours or requires outpatient IV hydration

Grading Headache:

Mild: No interference with activity
 Moderate: Repeated use of non-narcotic pain reliever > 24 hours or some interference with activity

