 Severe: Significant; any use of narcotic pain reliever or prevents daily activity

Grading Fatigue:

Mild: No interference with activity
 Moderate: Some interference with activity
 Severe: Significant; prevents daily activity

Grading Muscle Pain:

Mild: No interference with activity
 Moderate: Some interference with activity
 Severe: Significant; prevents daily activity

Grading Abdominal Discomfort/Pain:

Mild: No interference with activity
 Moderate: Some interference with activity
 Severe: Significant; prevents daily activity

Grading Joint Pain:

Mild: No interference with activity
 Moderate: Some interference with activity
 Severe: Significant; prevents daily activity

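### The sample diary grades chills on a different basis from the protocol's severity scale and records no severity for three local items, and no stated rule turns diary categories into grades

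*Combined protocol and SAP*

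**What the plan says.** Section 6.3.1 sets the list: "Solicited systemic AEs to be assessed include chills, nausea, vomiting, diarrhea, headache, fatigue, myalgia, abdominal discomfort/pain, joint pain, and fever". Appendix 1 has the participant mark chills as mild, moderate or severe on each of seven days, using a three-level key. The lowest level describes feeling cold and shivering. The middle level is "Moderate: Moderate tremor of entire body, medication taken". The top level, which is the one to compare with Grade 3, is "Severe: Prolonged or severe, does not respond to medication".

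Section 7.4.1 applies the 2007 toxicity grading guidance where that defines an event, and otherwise the protocol's own five-level scale. Its third level reads "Grade 3 = Severe: marked limitation in activity, some assistance usually required; medical intervention/therapy required, hospitalization possible".

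On the local page, items 6 to 8 begin with "6. Is there tingling or numbness at the injection site" and go on to bleeding and bruising. Each takes only Yes or No.

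Incidence and severity of solicited local and systemic events are phase 1 primary endpoints (Section 3.4.1.1) and phase 2 secondary endpoints (Section 3.4.2.2.1). Section 8.3.2 summarizes them by grade. Section 7.8.2 suspends vaccination under a rule that starts "If 3 or more participants report the same or similar Grade 3 solicited AE", subject to relatedness. Section 7.8.2.1 has a further three-participant rule for related events of Grade 3 or above.

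**The concern.** The daily record of a solicited symptom should let someone assign the grade that the protocol defines. For chills, the diary asks about something else and never asks what the chills stopped the participant from doing. For tingling or numbness, bleeding and bruising it asks nothing about severity.

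At stake is whether the by-grade tables for these events rest on the protocol's definition or on a mixture of diary category and later recollection. In phase 1, the counts that feed the two three-participant rules depend on the same grades.

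**Working it through.** No figure in the plan is in dispute, so the check compares texts.

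**1. Which protocol scale applies to chills.** Section 6.3.1 lists 10 solicited systemic events. Table 13 names six of them (nausea, vomiting, diarrhea, headache, fatigue, myalgia) and Table 12 grades fever. That leaves 10 − 6 − 1 = 3 without a named row: chills, abdominal discomfort/pain and joint pain. Two routes remain for these: the Section 7.4.1 scale, or the generic illness row that ends Table 13. The protocol does not say which.

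**2. The definitions side by side, at Severe or Grade 3.**

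| Source | Activity | Medication or intervention | Other |
|---|---|---|---|
| Appendix 1, chills | None | Medication has not worked | Prolonged or severe |
| Section 7.4.1 | Marked limitation | Intervention or therapy needed | Assistance usual; hospital care possible |
| Table 13, generic row | Daily activity stopped | Medical intervention needed | None |
| Appendix 1, abdominal and joint pain | Daily activity stopped | None | None |

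Both protocol routes contain an activity element, and the chills key has none at any level. Meeting the diary's Severe therefore does not establish Grade 3. Conversely, neither route requires that treatment fail, which the diary's Severe does. Neither definition contains the other. The diary wording also uses the word severe to define Severe and gives no length for prolonged.

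**3. Chills against the rest of the diary.** The other two systemic symptoms without a named row share an activity anchor: "Severe: Significant; prevents daily activity". Diarrhea is graded without activity, but that follows its own Table 13 row. Appendix 2 grades unsolicited events by interference with activity and asks separately what was done about them, including medication. Only the chills key replaces activity with medication use without a table row behind it.

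**4. Local items.** Tingling or numbness, bleeding and bruising have no row in Table 11. The diary gives no severity choice for them, while pain and itching on the same page have one.

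**5. From diary to grade.** Section 7.4 makes a qualified Investigator responsible for severity, and Section 6.3.1 takes solicited events from visits as well as the diary. No section states how diary Mild, Moderate and Severe become Grades 1, 2 and 3. The Investigator must supply the activity effect of chills, and the severity of items 6 to 8, from what the participant remembers.

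- After the first dose, Table 10 has in-office collection on day 8, so the recall period is short.
- In phase 2 arm 3, the second-dose diary is issued on day 29 and collected on day 60 (Table 10, note f). Its seven days end on day 35, so the nominal gap is 60 − 35 = 25 days. The only scheduled contact in between is the day 36 telephone call (note g).

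**6. Size.** The documents give no expected rate of chills, no share marked Severe and no rate of disagreement between diary and protocol grade. Without these, neither the shift in the by-grade tables nor the change in the chance of meeting a three-participant rule can be calculated.

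**The case against.** The strongest reply is that the diary does not set the grade. The Investigator does, sees participants on day 8 and can ask about activity then. Appendix 1 is labelled a sample. Concomitant medications, including analgesics for treatment-related events, are recorded under Section 6.8, so medication use is not lost. Nor is medication foreign to the protocol's grading: Table 11 uses it for pain, Table 13 for headache, and Section 7.4.1 refers to therapy. Finally, the Safety Review Committee reviews each treatment-related toxicity in the first seven days in phase 1, and each cohort once all 10 participants have completed that period. A chills report would therefore reach it whatever its grade.

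Most of this stands, and it rules out two stronger readings.

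- A reader might infer that diary Severe is entered as Grade 3 and so triggers false pauses or hides a signal. No section says so, and the committee's review is a safeguard that does not depend on the grade.
- A reader might infer that disabling but unmedicated chills are a missed Grade 3, or that chills persisting after medication without limiting activity are clearly Grade 1. Neither follows. Both protocol routes mention intervention at Grade 3, and Grade 1 in Section 7.4.1 excludes events that need it.

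Investigator grading does not supply a contemporaneous record of the activity effect of chills or of the severity of items 6 to 8. The sample form is also the only chills key in the documents.

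**Conclusion.** The point holds as a mismatch of definitions and a gap in data capture. The chills key lacks the activity element common to both candidate protocol scales, three solicited local events have no severity field, and no mapping from diary category to grade is stated. An effect on the severity endpoint and on the inputs to the phase 1 suspension rules is possible. Its size and direction are unknown, and assumed rates would not make them known.

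This rests on two assumptions: that the form is used substantially as printed, and that no mapping exists outside the text, for instance in the CRF completion guidelines mentioned in Section 7.4.3. The change is worth making because severity of these events is a phase 1 primary endpoint and the repair is cheap.

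**What to change.** 1. Reconcile the Appendix 1 chills key with the protocol grading, and state whether Section 7.4.1 or the generic row of Table 13 applies. Which definition of Grade 3 should feed the suspension rules is for the sponsor and the Safety Review Committee; this review does not choose one. Copying the joint-pain anchors would not by itself achieve alignment, because they omit the intervention element.
2. Have the diary record each day how far chills affected activity.
3. Add a mild/moderate/severe choice to local items 6 to 8.
4. State in Section 7.4.1 how diary categories map to grades for solicited events without a table row of their own. This would also cover abdominal and joint pain.

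The suspension thresholds do not change. The cost is a few more entries on a participant-facing form, a short addition to Section 7.4.1, and the IRB/IEC handling that Section 10.4 requires for an amendment.

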APPENDIX 2. SAMPLE DIARY FOR UNSOLICITED EVENTS

STUDY NUMBER*: _____

Patient Number*	Date of Vaccine Administration	/ /	*To be completed by the site
-----------------	--------------------------------	-----	------------------------------

Please complete this diary every day beginning on the day you receive the first dose of study vaccine until 30 days after you receive the last dose of study vaccine. Each page has space for recording 7 days of information. You will be provided with enough pages to last until 30 days after you receive the last dose of study vaccine. Be sure to bring this diary each time you visit the clinic and refer to this diary when study personnel contact you by telephone for schedule safety follow up assessments.

Unsolicited AEs	Date / /						

Please describe any unusual feelings of discomfort, signs or symptoms that are not specified on the other daily diaries. If you do not experience these feelings, signs, or symptoms, please mark "no additional symptoms to report". For each separate sign and symptom you report in the diary, please note the following:
 
 • How intense it is, either Mild (no interference with activity), Moderate (some interference with activity), or Severe (significant; prevents daily activity) • How long it lasts • Any actions you took to manage the symptoms (for instance, taking medication) 							

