3.4.1.1. Primary Endpoints

- Incidence of MAAEs and SAEs through 1 week post final vaccine administration
- Incidence of MAAEs and SAEs through 30 days post final vaccine administration
- Incidence of MAAEs and SAEs through 6 months post final vaccine administration
- Incidence and severity of solicited local reactogenicity AEs through 1 week after each vaccine administration
- Incidence and severity of solicited systemic reactogenicity AEs through 1 week after each vaccine administration
- Incidence and severity of unsolicited AEs through 1 week post final vaccine administration

- Incidence and severity of unsolicited AEs through 30 days post final vaccine administration
- Incidence of abnormal changes of laboratory safety examinations
- Changes in vital signs

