6.7.1.1. Medical History

At screening, the participant's medical history should be taken as per institutional standards. Otherwise, only the following medical history should be recorded in the eCRF:

- Current symptoms
- Items listed in inclusion/exclusion
- Existing medical conditions.
- Medications/procedures related to existing conditions.
- History of any prior COVID-19 symptoms.
- Vaccination history

Table 10: Schedule of Events: Previously Vaccinated/Infected Participants

Study Period	Prescreening ^a	Baseline/ Screening	Vaccine Administration and Initial Follow-Up					Extended Follow-Up		
			1	8	22	29	36	60	180	365
Study Day	-5 to -1	-5 to -1	1	8	22	29	36	60	180	365
Clinic visit number	Prescreening	Screening	1	2	3	4		5	6	7
Windows (Days)				± 3				± 7		± 14
General Assessments										
Informed consent	X	X								
Inclusion/ exclusion		X								
Demographics		X								
Medical history		X								
Tuberculosis screening ^b		X								
COVID-19 history of disease ^c		X	X	X	X	X		X	X	X
Confirm contraceptive measures		X	X			X				
Physical exam: height, weight ^d		X	X	X	X	X				
Vital signs ^e		X	X	X	X	X				
Concomitant medications		X	X	X	X	X		X	X	
Participant training on AE diaries			X							
Issue diaries for solicited AEs (phase 1 and 2 only) ^f				X			X			
Review and collect solicited AE diary (phase 1 and 2 only) ^f					X			X		
Issue diaries for unsolicited AEs				X						
Review unsolicited AE diary					X	X	X			
Collect unsolicited AE diary								X		

AAHI-SC2 and AAHI-SC3

ImmunityBio, Inc.

Clinical Trial Protocol: COVID-4.015 Version 4

Study Period	Prescreening ^a	Baseline/ Screening	Vaccine Administration and Initial Follow-Up						Extended Follow-Up		
			1	8	22	29	36	60	180	365	
Study Day	-5 to -1	-5 to -1	1	8	22	29	36	60	180	365	
Clinic visit number	Prescreening	Screening	1	2	3	4		5	6	7	
Windows (Days)			± 3					± 7		± 14	
In office AE collection			X	X	X	X		X			
Telephone follow-up							X ^g		X	X	
Vaccine Administration: Phase 1											
Cohort 1A			AAHI-SC2 (25 µg)								
Cohort 1B			AAHI-SC2 (50 µg)								
Cohort 1C			AAHI-SC2 (70 µg)								
Cohort 2A			AAHI-SC3 (25 µg)								
Cohort 2B			AAHI-SC3 (50 µg)								
Cohort 2C			AAHI-SC3 (85 µg)								
Vaccine Administration: Phase 2											
Experimental Arm 1			AAHI-SC2 (dose to be determined [TBD])								
Experimental Arm 2			AAHI-SC3 (dose TBD)								
Experimental Arm 3			AAHI-SC3 (dose TBD)				AAHI- SC3 (dose TBD)				
Control Arm			Janssen/Pfizer-BioNTech vaccine								

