Laboratory Assessments											

Study Period	Prescreening ^a	Baseline/ Screening	Vaccine Administration and Initial Follow-Up						Extended Follow-Up		
			1	8	22	29	36	60	180	365	
Study Day	-5 to -1	-5 to -1	1	8	22	29	36	60	180	365	
Clinic visit number	Prescreening	Screening	1	2	3	4		5	6	7	
Windows (Days)			± 3						± 7	± 14	
Chemistry panel ^h		X				X					
Hematology ⁱ		X				X					
Urinalysis ^j		X				X					
Biospecimens for SARS-CoV-2 ^k		X	X		X	X					
Collect whole blood for immunogenicity ^l			X	X					X		
Pregnancy test ^m		X	X				X				
Collect blood for SARS-CoV-2 serology	X										
HIV testing ⁿ	X										

^a If possible, the prescreening visit should occur on the same day as and immediately prior to the screening visit.

^b A TB symptom screening questionnaire per local guidelines will be used. If screening positive on questionnaire then sputum test and chest X-ray may be done to exclude the diagnosis of TB. If TB is excluded on these tests and the investigator considers that further TB testing is not clinically indicated then the potential participant may proceed with enrollment into the study. All potential participants suspected of having or with proven TB will be linked into care at their local clinic.

^c Potential exposure to SARS-CoV-2, symptoms of COVID-19, and outside testing results for SARS-CoV-2 infection will be collected at each assessment.

^d Physical examination will be performed at screening and symptom-directed (targeted) physical examination at all other time points if indicated. Height required at baseline/screening visit only.

^e Vital signs of temperature, heart rate, blood pressure, and respiratory rate will be assessed as indicated. Temperature will be documented at each visit and subsequently if clinically indicated.

^f Solicited AE diaries will be issued on day 29 and collected on day 60 only for participants in experimental arm 3 of the phase 2 study.

^g The telephone follow-up on day 36 is required only for participants in experimental arm 3 of phase 2 that get a boost on day 29.

^h See Table 9 for information on chemistry laboratory assessments.

ⁱ Hematology to include CBC with differential (5 part).

^j Urinalysis testing will include at a minimum protein, glucose, and presence of red blood cells. Sample collection should occur prior to vaccine administration.

^k Sample collection should occur prior to vaccine administration.

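### No contact is scheduled between days 60 and 180, so about two-thirds of the 6-month MAAE window (single dose) rests on one contact with no recall aid described, and the last month of arm 3's window is first reached at day 365

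*Combined protocol and SAP*

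**What the plan says.** - **Endpoint.** Section 3.4.1.1 lists among the phase 1 primary endpoints "Incidence of MAAEs and SAEs through 6 months post final vaccine administration". Section 3.4.2.2.1 lists the same item as a phase 2 secondary safety endpoint. The clock starts at the final dose, which is day 1 for most participants and day 29 for phase 2 arm 3 (section 3.3.1).
- **Contacts.** In Table 10 the row "In office AE collection" is marked at days 1, 8, 22, 29 and 60 and not later. The row "Collect unsolicited AE diary" has its only mark at day 60. The row "Telephone follow-up" is marked at days 36, 180 and 365, and footnote g adds: "The telephone follow-up on day 36 is required only for participants in experimental arm 3 of phase 2 that get a boost on day 29".
- **What is to be recorded.** Sections 6.3 and 7.2 require MAAEs and SAEs for 6 months, and related ones at any time.
- **What is to be asked.** Section 7.4.3 has the investigator ask about AEs and SAEs up to 30 days after the last dose. From then until 6 months it names SAEs only.
- **Diary.** Appendix 2 has participants write in the unsolicited diary up to 30 days after the last dose ("You will be provided with enough pages to last until 30 days after you receive the last dose of study vaccine"). It also asks them to "refer to this diary when study personnel contact you by telephone for schedule safety follow up assessments".

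**The concern.** An MAAE is defined in section 7.2 by an unscheduled medical visit. A non-serious one may come to the site's notice only if someone asks. After day 60 nobody is scheduled to ask for four months. When the contact does come, section 7.4.3 does not name MAAEs as something to ask about, and the plan describes nothing on which the participant could have noted a visit in the meantime.

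The reported MAAE percentages are at stake. Section 8.3.1 plans descriptive summaries and no statistical comparison of the phase 2 arms, so the observed incidence is itself the result. Visits that are forgotten or never asked about lower it directly. Arm 3 is also followed differently from the other arms in relation to its own 6-month window, so its MAAE figure would not be collected on the same footing as theirs.

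**Working it through.** The plan states no figure on this point, so there is nothing to reproduce. The check is day arithmetic on Table 10.

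**Inputs.** Last in-office AE collection is day 60; the next contacts are days 180 and 365 (Table 10). The final dose is day 1, or day 29 for arm 3 (section 3.3.1). Arm 3 has 30 of 180 planned participants (sections 3.2 and 8.4), leaving 180 − 30 = 150 with a single dose. Assumption: 6 months is M = 180 to 183 days.

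**Formulas.** Window end = dose day + M. Share after day 60 = (window end − 60)/M. Part left after day 180 = window end − 180.

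| | Single dose (day 1) | Arm 3 (final dose day 29) |
|---|---|---|
| Window ends | day 181 to 184 | day 209 to 212 |
| Share after day 60 | 121/180 = 67.2% to 124/183 = 67.8% | 149/180 = 82.8% to 152/183 = 83.1% |
| Left after day 180 | 1 to 4 days | 29 days (29/180 = 16.1%) to 32 days (32/183 = 17.5%) |

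The stretch between the two contacts is 180 − 60 = 120 days, and 120/180 = 66.7% (120/183 = 65.6%).

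**Visit windows.** With ±7 days at day 180, the gap is (173 − 63) to (187 − 57) = 110 to 130 days if day 60 carries ±3. It is (173 − 67) to (187 − 53) = 106 to 134 days if day 60 carries ±7. The single-dose share after the day 60 visit then runs from 114/180 = 63% to 131/183 = 72%.

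**Arm 3 tail.** The days after day 180 are next reached at day 365, which is 365 − 212 = 153 to 365 − 209 = 156 days after the window has closed. The inquiry period in section 7.4.3 has also ended by then.

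**Does the diary matter to the gap?** Entries stop 30 days after the last dose: day 31 for a single dose, day 59 for arm 3. Both fall before collection at day 60. So (180 − 30)/180 = 83% of anyone's window has no diary entries, whenever the diary is handed in. The form asks for symptoms, intensity, duration and actions taken, and has no field of its own for a medical visit.

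**Section 7.4.3 against sections 6.3 and 7.2.** For the period from 30 days to 6 months, the first names SAEs as the subject of inquiry, while the other two require MAAEs to be recorded. All three cannot describe one procedure.

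**Illustration only.** Assume a constant MAAE rate, full capture elsewhere, and recall r for days 60 to 180. The loss of *events* in single-dose participants is (120/182) × (1 − r) = 0.66 × (1 − r): about 7% at r = 0.9, 13% at r = 0.8 and 26% at r = 0.6. These values of r are assumptions; the documents give none.

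**The case against.** The strongest case on the other side has four parts.

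1. *The Appendix 2 sentence proves nothing about MAAEs.* This stands. A reader might infer that the gap arises because the diary is collected before the common telephone calls. The documents do not support that: the diary was never meant to cover days 60 to 180, and keeping it longer would not help. The sentence sits in a sample form, works as written at arm 3's day 36 call, and is merely idle for everyone else.
2. *Poor dating cannot do much harm.* This largely stands for single-dose participants. Their window ends at days 181 to 184, so nearly everything recalled at day 180 falls inside it. Dating at the 6-month boundary matters mainly for arm 3.
3. *Absence of an aid is inferred.* In part. Table 10 gives day 180 a clinic visit number while marking it as telephone follow-up, so the mode is unsettled. Concomitant medications and COVID-19 history are also taken then, which may jog memory. Section 7.2 says MAAEs follow the SAE collection guidelines, which could be read as a reporting route. However, the 24-hour SAE rule in section 7.5.2 starts from the investigator's knowledge and does not uncover events.
4. *The study is descriptive, and a log is a preference.* The 120-day gap and the conflict between section 7.4.3 and sections 6.3 and 7.2 remain whatever one thinks of logs.

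**Conclusion.** The point holds as one about the contact schedule. For up to 150 of 180 participants about two-thirds of the 6-month MAAE window rests on a single contact at day 180 (63% to 72% lies after day 60 once visit windows are allowed for). For the 30 in arm 3 about 83% lies after day 60 and is spread over two contacts, the second of them about five months after the window closes. It would be wrong to apply the two-thirds figure or a single recall to all 180.

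A reader might also conclude that MAAE incidence will be under-counted by 7% to 26%. The documents do not support that. The recall rates are assumed, and the figures concern events, whereas section 8.3.1 summarises participants. Someone with another captured MAAE still counts, so the loss in participant-level incidence would generally be smaller. Its size is unknown.

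The conclusion assumes that 6 months is 180 to 183 days and that the Table 10 marks fall in the columns given above, which should be confirmed against the formatted table. Footnote f, which places collection of arm 3's second solicited diary at day 60, supports that reading. This is a worthwhile low-cost improvement and does not threaten the study's validity.

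**What to change.** - At day 60, issue a one-page medical-visit log (date, type of visit, reason, hospitalized yes/no), to be kept until 6 months after the final dose.
- In Table 10, add issue of the log at day 60, and review of the log with a direct question about MAAEs at day 180. For arm 3, repeat the review at the existing day 365 contact, limited to events within 6 months of the second dose for this endpoint.
- Reconcile section 7.4.3 with sections 6.3 and 7.2 so that MAAEs are asked about through 6 months. State whether day 180 is a clinic visit or a call.
- Reword the telephone sentence in Appendix 2 so that the unsolicited diary is mentioned only for arm 3's day 36 call and the log is named for later contacts.

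Cost: one printed page, a few schedule entries and two reworded passages, carried by an amendment. No visit, call or sample is added. The downside is that reported MAAE incidence may be somewhat higher. If the log starts partway through, the report should say which participants had it.
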